5.4 Removal of Subjects from Therapy or Assessment

5.4.1 Discontinuation of Individual Subjects

Each subject has the right to withdraw from the study at any time. In addition, the investigator may discontinue a subject from the study at any time if the investigator considers it necessary for any reason, including the occurrence of an adverse event or noncompliance with the protocol.

Subjects with the following adverse events will be considered for treatment discontinuation:

- Severe or life-threatening allergic reactions will require the immediate interruption of ABBV-8E12 treatment, permanent discontinuation from further treatment and initiation of appropriate medical therapy and follow-up.
- Life-threatening drug related adverse events of nervous system will require discontinuation from further treatment with ABBV-8E12, initiation of appropriate medical therapy and follow-up.

All moderate and severe symptomatic neurological abnormalities and treatment-emergent MRI findings will be reported to AbbVie TA MD and subjects will be considered for discontinuation from treatment and may be permitted to continue in the study only after a management plan is discussed with the AbbVie TA MD.

Subjects with unexpected worsening of cognitive impairment or dementia will be reported to AbbVie TA MD and considered for discontinuation from treatment and may be permitted to continue in the study only after a management plan is discussed with the AbbVie TA MD.

Subjects at risk of suicide as indicated by answering yes to question 4 or 5 on the C-SSRS and/or determined by the investigator to be at risk of suicide should be discontinued from participation in the study and referred for appropriate follow-up care.

In the event that a subject withdraws or is discontinued from the study, the primary reason for discontinuation and any other reason(s) for the discontinuation from the study will be recorded and a physical examination, neurological examination, body weight, vital signs measurement, ECG, laboratory analyses, C-SSRS and an assessment of adverse events will be performed as soon as possible after discontinuation from the study. Additional blood samples for drug measurement may be collected at the time of discontinuation from subjects who are discontinued due to adverse events; the clock time, time in relation to dose, and date the sample was taken will be recorded.

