8.1.6 Safety Analyses

All safety analysis will be performed on the safety data set unless otherwise specified. Comparisons between each ABBV-8E12 dose group and placebo will be performed with two-sided test at the significance level of 0.05, if applicable. Pairwise comparisons for each ABBV-8E12 dose group versus placebo will be evaluated.

All safety assessments that are taken no more than 20 weeks after the last dose of study drug will be included in the safety evaluation for subjects who complete the double-blind Treatment Period or PD and do not roll over to the planned extension study. If subjects enroll in the planned extension study, their safety information collected before the first dose of the planned extension study will be included in the safety evaluation for the double-blinded period.

Study Drug Exposure and Compliance

The number of doses on study drug will be summarized by treatment group and all treatment groups combined. The number and percentage of subjects with at least 90% compliance with study drug (i.e., complete 90% of scheduled doses) will be summarized by treatment group and all treatment groups combined.

Adverse Events

A treatment-emergent adverse event (TEAE) is defined as any adverse event that begins or worsens in severity on or after the first study drug dose date and no more than 20 weeks after the last study drug dose date.

Unless otherwise specified, the treatment group differences in continuous safety variables (e.g., change from baseline to final observation on laboratory tests) will be assessed using an ANOVA model with the term of treatment, and the treatment group differences in binary safety variables will be evaluated using a Fisher's exact test.

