11.6.3 Summary of MRI Safety Evaluations

MRI safety evaluations will be summarized and compared between each ABBV-8E12 dose and placebo based on MRI evaluations in the double-blinded period. The summaries include number and percentage of subjects with presence and severity of baseline and post baseline MRI findings of cerebral edema, microhemorrhages, and severe white matter disease as defined by a score of 3 on Age-Related White Matter Changes (ARWMC) scale and other structural abnormalities. Descriptive statistics (mean, median, minimum, maximum) of number of new microhemorrhages or new lesions in the double-blind period will be presented. Listing of subjects with post-baseline MRI findings will be provided. No comparison will be performed for MRI safety summary.

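### SAP 11.6.3 does not specify how many subjects per arm have a new or worsened MRI finding, and the planned lesion statistics cannot supply that number

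*SAP*

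**What the plan says.** SAP 11.6.3 plans three outputs.

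- Subject-level counts: "number and percentage of subjects with presence and severity of baseline and post baseline MRI findings of cerebral edema, microhemorrhages", then severe white matter disease (a score of 3 on the ARWMC scale) and other structural abnormalities.
- Lesion-level statistics: "Descriptive statistics (mean, median, minimum, maximum) of number of new microhemorrhages or new lesions in the double-blind period will be presented".
- A listing: "Listing of subjects with post-baseline MRI findings will be provided".

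The section opens with "MRI safety evaluations will be summarized and compared between each ABBV-8E12 dose and placebo" and closes with "No comparison will be performed for MRI safety summary". Protocol 8.1.6 has no MRI-specific analysis. Its general rule is that, unless otherwise specified, "the treatment group differences in binary safety variables will be evaluated using a Fisher's exact test".

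The protocol does recognise new MRI findings as a category of their own. Section 5.4.1 states: "All moderate and severe symptomatic neurological abnormalities and treatment-emergent MRI findings will be reported to AbbVie TA MD". Section 6.1.6.2 uses the same category.

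**The concern.** For a safety imaging table the natural question is how many subjects on each dose developed something on MRI that they did not have at baseline, or had to a lesser degree. None of the three outputs is specified to answer it. In the first, a subject whose finding was already there at screening and is still there counts after baseline exactly like a subject whose finding is new. The second isolates new lesions but describes lesions, not subjects. The third covers every subject with a finding after baseline and is not said to separate new from old.

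Long-term safety is a primary objective, and MRI is a named safety variable (Protocol 5.3.4, SAP 4.6). The study report could therefore lack the one MRI count that maps onto the protocol's own category of treatment-emergent findings.

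**Working it through.** The plan gives no MRI rate or figure, so there is nothing to reproduce. Three checks follow.

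**1. Can the number of affected subjects be recovered from the planned new-lesion statistics?** Take an arm of 100 (the planned group size, SAP 4.3).

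- Arm A: one subject with 5 new lesions, five with 1 each, 94 with none. Mean = (5 + 5×1)/100 = 0.10.
- Arm B: two subjects with 5 each, 98 with none. Mean = (2×5)/100 = 0.10.

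In both arms the median is 0, the minimum 0 and the maximum 5. The affected subjects number 6 and 2. The four statistics are identical for a threefold difference, so the answer is no. This needs no assumed rate. The median is 0 whenever fewer than half of an arm is affected.

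**2. How do the other safety sections treat abnormality at baseline?**

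| Section | What is counted |
|---|---|
| SAP 11.3.3 laboratory | meets the criterion and is more extreme than baseline |
| SAP 11.4.2 vital signs, weight | same |
| SAP 11.5.2 ECG | same |
| SAP 11.2 adverse events | begins or worsens on or after first dose |
| SAP 11.6.3 MRI, subject level | presence and severity at baseline and after baseline |

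MRI is the exception.

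**3. What does counting post-baseline presence do to a true difference?** Let b be the baseline prevalence and q the proportion of subjects who gain a new finding. Assume that findings persist and that q is the same with or without a finding at baseline. Then

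post-baseline presence = b + (1 − b)q, and
difference between arms = (1 − b)(q_dose − q_placebo).

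The values of b and q are assumptions. With q = 3% on placebo and 12% on a dose:

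| b | Presence, placebo | Presence, dose | Difference (points) | Ratio |
|---|---|---|---|---|
| 0% | 3.0% | 12.0% | 9.0 | 4.00 |
| 10% | 12.7% | 20.8% | 8.1 | 1.64 |
| 20% | 22.4% | 29.6% | 7.2 | 1.32 |
| 30% | 32.1% | 38.4% | 6.3 | 1.20 |

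With q = 5% and 15%, the ratio falls from 3.0 to 1.62, 1.33 and 1.21 at b = 10%, 20% and 30%. With 2% and 10%, it falls from 5.0 to 1.61, 1.30 and 1.18. At b = 0 nothing is lost.

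Baseline counts are in the same summary. Under persistence, and if the same subjects are scanned, post-baseline minus baseline is (1 − b)q. At b = 20% that is 22.4 − 20 = 2.4 per 100 on placebo and 29.6 − 20 = 9.6 on the dose, which restores the ratio of 4. It omits subjects with an old finding who gain more: bq = 0.6 and 2.4 per 100.

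**The case against.** The strongest reply is that the information is largely there. It has several parts.

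- **The plan does separate new from old.** It counts new lesions as new, and the mean is informative. If affected subjects have on average 4 new lesions (an assumption), 3% versus 12% affected gives expected means of 0.03×4 = 0.12 and 0.12×4 = 0.48. In 20,000 simulated trials with geometric counts, the dose mean exceeded the placebo mean in 97%. This stands. It is a reason to keep those statistics, but they still do not give the number of subjects.
- **Adverse event tables.** A new or worsened finding recorded as an adverse event is counted per arm by preferred term (SAP 11.2.2). The definition in Protocol 6.1.1.1 is wide enough to allow this, but neither document requires every new MRI finding to be recorded as one.
- **Netting against baseline, or a hand count from the listing.** The wording could be programmed as a shift table, and the listing's columns are not fixed. Either would help; neither is specified. Netting also has the limits shown above.
- **Eligibility.** Exclusions 5 and 6 and the screening MRI text in Protocol 5.3.1.1 should lower baseline prevalence for several finding types, and only severe white matter disease is tabulated. This stands too. Microhemorrhages are not named in those criteria, so dilution is plausible mainly there.
- **Protection during the trial.** The DMC reviews unblinded safety data (Protocol 8.1.10, SAP 4.4), and treatment-emergent findings go individually to the sponsor's physician. The point therefore concerns end-of-study reporting.

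A reader might infer that the count will never be produced, or that old lesions dilute every MRI signal. The documents support neither. The count is unspecified rather than ruled out, and dilution requires baseline findings that are common and persist.

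**Conclusion.** The gap is real and narrow. SAP 11.6.3 does not specify n (%) of subjects per arm with a new or worsened MRI finding, and the mean, median, minimum and maximum of new lesions cannot replace it. That conclusion rests on the text and on the two-arm example, and needs no assumed rates. It is out of line with the SAP's own laboratory, vital sign and ECG summaries and with the protocol's category of treatment-emergent MRI findings.

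The size of any dilution is unknown. It is the factor (1 − b) on the absolute difference, given persistence and equal incidence with and without a baseline finding, and the documents give neither b nor q. A loss of test power is a tempting way to express it, but the section's last sentence says that no comparison will be made, so a power figure would describe a test that may not exist.

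This is a cheap improvement to the safety reporting. It does not show that a signal would be missed.

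**What to change.** In SAP 11.6.3:

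1. Define a treatment-emergent MRI finding as one absent at baseline, or greater in number or severity than at baseline, on any double-blind scan. Using any scan matters because the window rule in SAP 6.2 keeps one observation per visit window.
2. Tabulate n (%) of subjects with at least one such finding, by type (edema, microhemorrhage, white matter disease, other structural abnormality), for each dose, ABBV-8E12 Overall and placebo. The denominator is subjects with a baseline and at least one post-baseline MRI.
3. Keep the planned lesion-count statistics.
4. Flag new versus pre-existing in the listing.
5. In the same edit, reconcile the opening sentence (doses compared with placebo) with the closing sentence (no comparison), and state whether the Fisher default in Protocol 8.1.6 applies.

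The cost is SAP wording, one table and a listing flag. Baseline and post-baseline readings are already planned, and the existing new-lesion statistics already require new lesions to be identified for each subject. The downside is a little more programming.

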12.0 Pharmacokinetic Analysis

12.1 Determination of Values of Pharmacokinetic Parameters

C_{\max} for a dose interval will be the maximum observed concentration after the beginning of infusion of the dose and before the beginning of infusion of the next dose. T_{\max} will be the time of C_{\max} relative to the beginning of infusion. The values of C_{\max} and T_{\max} will be considered missing if there is no measurement from a sample obtained before 3 hours after the end of infusion.

AUC for a dose interval will be obtained using straight lines between adjacent concentrations for times before 4 hours after the end of infusion. An exponential curve will be used between the last time point of measurement before 4 hours after the end of infusion and the first time point of measurement after 4 hours after the end of infusion, and an exponential curve will be used between adjacent time points of measurement in the dose interval that come after this. Actual times relative to the beginning of infusion will be used in the calculation of AUC.

The scheduled length of the first and fourth dose intervals is 672 hours. If the actual length of a dose interval differs from the scheduled length by more than an hour, a value for the ABBV-8E12 concentration at the scheduled end of the dosing interval (672 hours after the start of infusion of the dose at the beginning of the dose interval) will be imputed. In this case, the AUC will be calculated using the imputed value at the scheduled end of the dosing interval. The imputed value will be obtained from interpolation with, or extrapolation of, the exponential curve defined by the last two concentration measurements in the dosing interval.

For the first dose interval, the concentration at the beginning of infusion of the dose will be assumed to be 0 even if the scheduled pre-dose blood sample is mistakenly obtained after the beginning of infusion. For the fourth dose interval, the concentration of the pre-dose sample will be used as the concentration at the beginning of infusion of the dose provided that the blood sample is obtained in the 30 minute interval before the beginning of infusion. If the blood sample is obtained earlier than 30 minutes before the beginning

of infusion, for the calculation of AUC the concentration at the beginning of infusion will be $C_{obs} \times e^{-\beta t}$, where C_{obs} is the reported measurement for the pre-dose concentration, β is the rate constant determined from the exponential curve defined by the last two concentrations in the third dose interval and t the length of the time interval between the pre-dose blood sample and the beginning of infusion. If the pre-dose sample for the fourth dose interval is mistakenly obtained after the beginning of infusion of the dose, a value for the concentration at the beginning of the dose interval (beginning of infusion) must be imputed unless the sample was obtained within a very few minutes of the beginning of infusion (< 15 minutes). The other subjects in the same treatment group who have values for the concentrations at the beginning of the fourth dose interval, the beginning of the third dose interval and the end of the fourth dose interval may be used to obtain a linear regression model for the concentration at the beginning of the fourth dose interval, with the concentrations at the beginning of the third dose interval and the end of the fourth dose interval as explanatory (predictor) variables. The missing value may be replaced by the predicted value from the regression model.

12.2 Tabulations and Summary Statistics

For the data of Cohort 1, serum concentrations of ABBV-8E12 and pharmacokinetic parameter values will be tabulated for each subject and each dose level, and summary statistics will be computed for each sampling time and each parameter by dose level. Also, for the serum concentration data of all subjects, summary statistics will be provided for each scheduled time of sampling with breakdown by dose level.

CSF concentration data after the fourth dose and the final dose will be tabulated and summarized by dose level.

Summary statistics will consist of: number of observations (n), mean, standard deviation, coefficient of variation as a percentage (quotient of standard deviation and mean, multiplied by 100), minimum, median and maximum. In addition, the geometric mean will be given for C_{max} and AUC.

12.3 Model and Tests

Unless stated otherwise, hypothesis tests will be performed at significance level 0.050.

Change in Concentration with Repeated Dosing

The concentration data of the planned pre-infusion sampling times of Cohort 2 during Weeks 4 through 72 will be analyzed to investigate change in serum concentration over time. The data of Cohort 1 will also be included in this analysis. The logarithmic transformation will be used unless the data show that the logarithm has substantial non-symmetry (e.g., magnitude of skewness coefficient > 1.0) while untransformed concentration or another transformation has an approximately symmetric distribution. A MMRM analysis will be performed. The model will have fixed effects for dose level, classification by time and the interaction of dose level and time. The subjects will be viewed as a random sample, and an appropriate structure will be selected for the covariance matrix of the observations from a subject. The concentration central value (back transformation of the estimate of the mean of the transformed data) versus time curves for the three dose levels will be plotted on the same graph.

Dose Proportionality

Analyses to address the issue of dose proportionality will be performed on the data of Cohort 1. An analysis will be performed on each of dose normalized C_{\max} and dose-normalized AUC for each of the first and fourth dose intervals. An analysis will also be performed on dose-normalized C_{trough} at Week 16. The logarithmic transformation will be employed for C_{\max} and AUC and will likely be used for C_{trough} . An analysis of covariance (ANCOVA) will be performed for each exposure variable, with the greater emphasis on the fourth dose interval. Subjects will be classified by dose level, and body weight will be a covariate. Other variables such as age and sex that might explain some of the variability among subjects will be considered. Except for body weight, a necessary condition for a variable to be included as a covariate in the final model is that the regression coefficient be significant at level 0.100. The dependence among explanatory variable candidates will

also be considered when selecting the final model. Within the framework of the final model, the hypothesis of no difference between the means of the highest and lowest doses will be tested. If this hypothesis is rejected, corresponding tests will be conducted for the comparison of the middle dose to the lowest and highest doses.

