The concentration data at the end of the first four dose intervals in Cohort 1 will be summarized to investigate the change in serum concentration with repeated dosing. The logarithmic transformation will be used if appropriate. The model will have effects for dose level, week and the interaction of dose level and week. For measures of exposure, an analysis of covariance will be performed on dose normalized parameters of Cohort 1. It is anticipated that the logarithmic transformation will be employed. Subjects will be classified by dose level. Body weight will be a covariate, and there may be other covariates. The hypothesis of dose proportionality will be tested within the framework of the model by testing the hypothesis of no difference between the highest and lowest doses. Population pharmacokinetic analyses will be performed using a non-linear mixed-effect modeling approach with the nonlinear mixed effect modeling (NONMEM) software (version VII, or higher version). The structure of the starting pharmacokinetic model will be based on the pharmacokinetic analysis of data from previous studies and Cohort 1 of this study. Apparent CL and V of ABBV-8E12 will be the pharmacokinetic parameters of major interest in the NONMEM analyses.

CSF concentration data after the fourth dose and the final dose in Cohort 1 and Cohort 2 (if available) will be tabulated and summarized by dose level.

Immunogenicity:

The anti-drug antibody (ADA) titers will be tabulated by dose level and summarized as appropriate.

Biomarker:

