5.0 Investigational Plan

5.1 Overall Study Design and Plan: Description

This Phase 2 multiple dose, multicenter, multinational, randomized, double-blind, placebo-controlled study is designed to evaluate the efficacy and safety of ABBV-8E12 in subjects with Early AD. Subjects will be allowed to use medications to treat symptoms related to AD, if on a stable dose for at least 12 weeks prior to randomization. The study will consist of a screening period of up to 12 weeks, a 96-week double-blind treatment period and a follow-up period of approximately 20 weeks following the last study drug administration (for those subjects who prematurely discontinue from treatment, decline to participate in or do not qualify for extended treatment). At the end of the treatment period, eligible subjects who completed the 96-week treatment period may enter a planned separate extension study for extended treatment. All activities for these subjects will be outlined in a separate extension study protocol.

Approximately 400 subjects with Early AD between 55 to 85 years of age will be eligible to participate in the study according to the selection criteria described in Section 5.2. Upon completion of screening and baseline procedures, eligible subjects will be randomized to one of the 3 ABBV-8E12 dose arms (300 mg, 1000 mg or 2000 mg) or

placebo in a 1:1:1:1 ratio. Doses will be administered every 4 weeks via IV infusion. Refer to Section 5.5.1 for details on infusion times.

This study will utilize a Data Monitoring Committee (DMC). The DMC will consist of at least 2 non-AbbVie clinicians, at least 1 non-AbbVie statistician, and at least 1 external pharmacokineticist. The DMC will review unblinded safety data and make recommendations based on the emerging safety profile of ABBV-8E12 and on the results of the interim efficacy analyses. The DMC membership, responsibilities and operating logistics will be documented in a charter that will be finalized prior to the first DMC review meeting.

Safety and tolerability will be monitored throughout the study.

The first 48 subjects enrolled into the study will be represented as Cohort 1 in this protocol while the subjects enrolled subsequently to Cohort 1 will be represented as Cohort 2. More frequent pharmacokinetic (PK) sampling and safety monitoring by the DMC will be conducted for Cohort 1-subjects (Table 1).

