4.2 Study Design

This Phase 2 multiple dose, multicenter, multinational, randomized, double-blind, placebo-controlled study is designed to evaluate the efficacy and safety of ABBV-8E12 in subjects with Early AD. Subjects will be allowed to use medications to treat symptoms related to AD, if on a stable dose for at least 12 weeks prior to randomization. The study will consist of a screening period of up to 12 weeks, a 96-week double-blind treatment period and a follow-up period of approximately 20 weeks following the last study drug administration (for those subjects who prematurely discontinue from treatment, decline to participate in or do not qualify for extended treatment). At the end of the treatment period, eligible subjects who completed the 96-week treatment period may enter a planned separate extension study for extended treatment. All activities for these subjects will be outlined in a separate extension study protocol.

Approximately 400 subjects with Early AD between 55 to 85 years of age will be eligible to participate in the study according to the selection criteria described in protocol Section 5.2. Upon completion of screening and baseline procedures, eligible subjects will be randomized to one of the 3 ABBV-8E12 dose arms (300 mg, 1000 mg or 2000 mg) or placebo in a 1:1:1:1 ratio. Doses will be administered every 4 weeks via IV infusion.

This study will utilize a Data Monitoring Committee (DMC). The DMC will consist of at least 2 non-AbbVie clinicians, at least 1 non-AbbVie statistician and at least 1 external pharmacokineticist. The DMC will review unblinded safety data and make recommendations based on the emerging safety profile of ABBV-8E12. The DMC will review the results of the interim efficacy analyses. The DMC membership, responsibilities and operating logistics will be documented in a charter that will be finalized prior to the first DMC review meeting.

Safety and tolerability will be monitored throughout the study. The first 48 subjects enrolled into the study will be represented as Cohort 1 in this protocol while the subjects enrolled subsequently to Cohort 1 will be represented as Cohort 2. The protocol Amendment 2 states that Japanese subjects enrolled in J1 would follow safety and PK

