5.1 Variables Used for Stratification of Randomization

Subject randomization is stratified by study site.

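### Dose proportionality is assessed by a difference test in about 12 subjects per dose, with no interval for the dose-normalized ratio, so a non-significant result cannot support proportionality

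*SAP*

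**What the plan says.** The Protocol synopsis sets the criterion: "The hypothesis of dose proportionality will be tested within the framework of the model by testing the hypothesis of no difference". The comparison is 2000 mg against 300 mg. Protocol 8.1.7.2 repeats the test. SAP 12.3 limits it to one cohort: "Analyses to address the issue of dose proportionality will be performed on the data of Cohort 1". The responses are dose-normalized Cmax and AUC in the first and fourth dose intervals and dose-normalized Ctrough at Week 16. They are analysed by ANCOVA with body weight as a covariate and possibly others, on the log scale for Cmax and AUC and probably for Ctrough. In the final model "the hypothesis of no difference between the means of the highest and lowest doses will be tested", at level 0.050.

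The SAP then says what follows a rejection: "If this hypothesis is rejected, corresponding tests will be conducted for the comparison of the middle dose to the lowest and highest doses". It does not say what follows a non-rejection. Neither document gives a margin, a power figure, a CV, or a confidence interval for the dose-normalized ratio.

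SAP 12.2 does plan summary statistics by dose level for each parameter, with geometric means for Cmax and AUC.

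**The concern.** A test whose null hypothesis is proportionality can give evidence against it but not for it. A non-significant result may mean that exposure is close to proportional, or only that the sample was too small or too variable to show otherwise. Without an interval the reader cannot tell which. The 1000 mg dose gets no formal comparison at all unless the extreme doses differ significantly.

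The omission stands out against the documents' own practice. Protocol 8.1.7.2 plans a 95% confidence interval for the accumulation ratio directly after the dose-proportionality text. SAP 11.3.1, 11.4.1 and 11.5.1 plan 95% intervals for the pairwise contrasts in laboratory, vital sign and ECG changes.

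At stake is what can be said on a secondary objective, pharmacokinetics. The dose rationale in the Protocol simulated exposure and safety margins on the assumption of linear pharmacokinetics, and this analysis is the SAP's formal check of that assumption.

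**Working it through.** The plan states no power or sample size for this analysis, so there is no figure to reproduce.

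**Inputs from the documents**
- Cohort size (Protocol 5.1): "The first 48 subjects enrolled into the study will be represented as Cohort 1".
- Allocation (SAP 4.2): three active doses "or placebo in a 1:1:1:1 ratio", so 48/4 = 12 expected per dose.
- Stratification (SAP 5.1): "Subject randomization is stratified by study site". No cohort stratum is named, so 12 is an expectation and not a guarantee.
- Level 0.05 (SAP 12.3).

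**Assumptions**
- The test is two-sided. The two-sided default in SAP 6.1 names efficacy and safety, not pharmacokinetics.
- Between-subject CV is 20% to 40% in the main calculation, with higher values as a check.
- As a pessimistic case, 9 subjects per dose are evaluable: 12 × (1 − 0.25). The 25% is borrowed from the efficacy sample-size statement in SAP 4.3.

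**Formulas**
- SD on the log scale = √ln(1 + CV²)
- SE of the log ratio = SD × √(2/n)
- Residual df = 3n − 4 (three active doses and one covariate), which is 32 at n = 12
- Power from the noncentral t distribution with noncentrality ln(ratio)/SE

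**Worked case, CV 30%, n = 12, ratio 1.25.** SD = √ln(1.09) = 0.294. SE = 0.294 × √(2/12) = 0.120. Noncentrality = ln(1.25)/0.120 = 0.223/0.120 = 1.86. Power = 44%.

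**Results at n = 12 per dose** (departures in either direction, for example 1.25 or 0.80)

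| Assumed CV | Power, 1.25-fold | Power, 1.5-fold | Power, 2-fold | Ratio detectable with 80% power | Expected 90% CI: estimate ×/÷ |
|---|---|---|---|---|---|
| 20% | 76% | >99% | 100% | 1.27 | 1.15 |
| 30% | 44% | 91% | 100% | 1.41 | 1.23 |
| 40% | 28% | 71% | 99% | 1.58 | 1.31 |

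At higher assumed CVs, power for a 2-fold departure is 94% (CV 50%), 84% (CV 60%) and 65% (CV 80%).

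Power falls below 50% at a CV of about 28% for a 1.25-fold departure, 53% for 1.5-fold and 100% for 2-fold. With 9 per dose these thresholds become about 24%, 44% and 83%. At CV 30% with 9 per dose, power is 34% for 1.25-fold and 80% for 1.5-fold.

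**Scale of the departures.** The dose range is 2000/300 = 6.67-fold. If exposure follows dose to the power b, the dose-normalized ratio is 6.67^(b − 1): 0.83 for b = 0.9 and 0.68 for b = 0.8.

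**What a fixed equivalence margin would do** (margins assumed, exposure exactly proportional, n = 12; chance that the 90% CI lies inside the margin)

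| Margin | CV 20% | CV 30% | CV 40% |
|---|---|---|---|
| 0.80–1.25 | 71% | 16% | 1% |
| 0.70–1.43 | 99% | 80% | 43% |

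**The case against.** A reader might go further than the documents allow in four ways.

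1. *Large departures would usually be missed.* The calculation does not support this. At CVs of 30% to 40% a 1.5-fold departure is detected about 71% to 91% of the time and a 2-fold departure at least 99%. A 2-fold departure would usually be missed only at a CV near 100%.
2. *A non-significant result will be declared proportional.* Neither document says so. The synopsis labels this the test of proportionality but attaches no conclusion to non-rejection. The gap is that no reading is given.
3. *The plan gives no estimate at all.* SAP 12.2 gives geometric means by dose for Cmax and AUC, so unadjusted ratios for those two can be worked out by dividing by dose. They are not adjusted for weight and carry no interval, and no geometric mean is planned for Ctrough.
4. *Exposure-response work or dose choice depends on this test.* No passage makes that link. SAP 3.0 places population pharmacokinetics and exposure-response outside the SAP. Equally, Protocol 8.1.7.4 says those analyses may not be run on this study's data alone, so they are not an assured substitute.

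Two further defences have some force. SAP 12.3 also models pre-infusion concentrations from Weeks 4 to 72 in both cohorts with dose-level effects, which uses far more subjects, although it is framed as change over time. Restricting Cmax and AUC to Cohort 1 follows from the sampling, since only Cohort 1 has post-infusion samples. Finally, covariate adjustment may lower the residual SD, so power at a given between-subject CV could be higher than shown.

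**Conclusion.** The point holds as a limit on what can be concluded. The planned test can reject proportionality but not support it, and no interval or adjusted ratio is planned to fill the gap. Departures of about 25% could easily be missed: power is about 76%, 44% and 28% at CVs of 20%, 30% and 40%, and below one half once the CV reaches about 28%. Departures of 2-fold would almost always be found at those CVs.

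These figures rest on an assumed CV, a two-sided test and the expected 12 subjects per dose. The lack of an interval and of any rule for non-rejection does not depend on them. This is a worthwhile refinement to a secondary pharmacokinetic analysis, and the primary efficacy conclusion is not affected.

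**What to change.** Amend the dose-proportionality text of SAP 12.3 as follows.

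- From the ANCOVA already planned, report geometric mean ratios of dose-normalized Cmax, AUC and Ctrough for 2000 versus 300 mg and for 1000 versus 300 mg, each with a 90% confidence interval, whatever the test shows. If Ctrough is not log-transformed, give the corresponding estimate and interval on the scale used.
- Base the statement on proportionality on these estimates and intervals.
- State that failure to reject is not evidence of proportionality.
- Do not impose a strict 0.80–1.25 criterion. At this sample size it would be close to unattainable unless the CV is about 20%.

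The cost is SAP wording and a few more lines of output. No new data or model is needed. The downside is that the conclusion may often have to be stated as inconclusive. Without a margin it also remains a judgement on the width and position of the intervals.
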